#### Baseline Data from Primary Schools

Primary schools will be asked to provide the names of the secondary schools where most of their children move on to and the proportion of children in their school who receive Free School Meals (FSM), and the proportion of eligible children who receive Free School Meals

#### Recruitment of Secondary Schools

All secondary schools which have participating primary schools in their catchment area, or which have been identified by primary schools will be sent an invitation letter and information sheet. Secondary schools will be able to contact the trial co-ordinators should they have further questions. We will ask secondary school head teachers to sign and return a written consent form to allow us to follow up participating children who move to their schools in the later years of the study.

#### Baseline Data from Secondary Schools

No baseline data will be required from secondary schools.

#### **Recruitment of Parents**

We will ask each school to post out a 'CLASS Trial Information Pack' to all parents of eligible children. Each pack will contain a covering letter from the school (if they chose to insert one), , a user-friendly information sheet for parents/carers, including the Parent/Carer Withdrawal Form. The Information Sheet will explain the purpose of the CLASS trial and what taking part would entail. Contact details for the trial coordinators will also be provided should parents have further questions. A short DVD clip for parents explaining the trial will also hopefully be produced.

We will be guided by schools on the need to provide the documentation in other languages and will work with schools to provide this wherever possible. Schools may also meet face to face with or phone some parents if they feel this would be more appropriate.

We will ask parents to discuss the trial with their child/children. If either parents or children are unwilling or unable to take part in the study, we will request parents to send us a withdrawal form in a self-addressed envelope or call/text/email us on the contact details provided within the information pack. Parents and children will be consented before we collect any baseline data and randomise schools to minimise recruitment bias. Just before data collection, we will send another reminder one-page letter to parents (of children for whom no withdrawal forms have been received), requesting them to either call/text/email us or send us a withdrawal form if they like to withdraw their child/children from the study at any stage.

In schools allocated to the intervention group, all participating children (in years 5 and 6 in the 2011/2012 school academic year) will take part in the SFH activities. We will ask schools to let us know which participating children were absent for the activities..

#### Recruitment of Children

All the children participating in this trial will be under 16 and therefore we will seek parental/carer consent as above for them to take part. However we feel that at the time of recruitment the children will be of an age (9 to 11 years) where they are able to understand, to some degree, the research. Children will therefore be provided with an age appropriate information sheet, which will be given

out to them at school. We will ask the teachers to take the children through the information sheet and answer any questions the children may have. We will also provide schools with a short DVD clip which can be shown to the children in school describing the research. The children will be encouraged to discuss the research with their parents. If children are unwilling or unable to take part in the study, they can either let their teachers or parents know, as they feel appropriate. We hope this will also ensure the children's commitment to the project. All participating children will be allocated a unique identification number and a register linking this number with other identifiable details will be kept on secure password protected computers or at YTU in a locked cabinet separate from all other data collection forms.

#### Baseline Data from Children

Each primary school will be sent a children's survey (paper form) for each child to complete assessing the level of smoking restrictions at home, their own attitude towards smoking, the smoking behaviour of adults in their home and their quality of life (SO1, SO2, SO3, SO4). The school will be asked to oversee the completion of the survey and return completed surveys to the YTU. Each school will also be sent a container for each child in which each child will be asked to provide a saliva sample. The school will be asked to return the saliva samples to a laboratory for testing (PO). The children's survey and the saliva samples will be anonymised and when completed and returned will have nothing that can identify the child's name or address. Saliva samples will be destroyed immediately after cotinine testing and recording of their results in the database. The database entries will also be anonymous containing only children's unique identification number. All information will be kept completely confidential.

Primary schools will be asked to provide the following baseline data about each child taking part in the study:

- Gender
- DOB
- Ethnicity
- 12 month attendance records for participating children including reasons for absence if known (SO5)
- Free School Meal status of participating children

## **Randomisation**

Once necessary baseline data has been logged into a database, the participating schools will be randomly allocated to each of the two arms, intervention and control on an equal basis (i.e. 25 schools in each arm). Each intervention school will be paired with a control school for follow up purposes. We will not use simple randomisation, because this may cause cluster level imbalances. We will use a restricted method of allocation called minimisation, which achieves balanced groups more efficiently than other allocation methods. We will minimise (i.e., ensure balance) on size of eligible sample and proportion of eligible children receiving Free School Meals (which is a proxy for socioeconomic status).

There is a possibility of potential contamination through siblings attending different primary schools. For example one sibling may be at a school allocated to be in the intervention arm and another sibling may be at school allocated to be in the control arm. In this example the child attending the control school and their parent/carer would be contaminated with the intervention from the child attending the intervention school. However, it is unusual to have siblings in different primary schools; therefore it is unlikely to be an issue in a vast number of cases.

## **Trial Intervention**

#### **Intervention Group**

Schools in the intervention arm will receive SFH when the participating children are in Years 5 and 6. SFH is a school-based intervention to encourage families to implement smoking restrictions in their homes and, as a consequence, to protect children and non-smokers from SHS. A trained SFH project worker will visit each school and take Years 5 and 6 children (on two separate occasions if necessary) through a series of educational activities using a SFH toolkit. Children, whose parents asked for their children to be withdrawn from this study, will continue to attend their regular classes or appropriate provision will be made.

The SFH activities consist of a class-room presentation and activities lasting approximately two hours. Children will be given a promise form which contains pictorial and written messages on the hazards of SHS, a pictorial step-guide for families to make their homes smoke free, a puzzle to help families learn about the benefits of a smoke free home and a tear-off slip to make a commitment to impose smoking restrictions at home. Children are expected to bring this slip back to school and receive a SFH Gold certificate should their home be totally smoke free. These activities are designed to raise awareness among children about the hazards of SHS and empower them to negotiate smoking restrictions with other family members at home. Families are encouraged to "sign-up" to a voluntary contract not to allow smoking inside their houses and in front of children. In addition; (a) school teachers will be offered a training session on SFH to help them in reinforcing SFH messages, (b) a brief session on SFH for all children through a whole school assembly, could be supported by the SFH co-cordinator at the schools request. A detailed description of the intervention is available in a report titled "Smoke Free Homes Campaign Report"(41).

#### Data Collection

Schools will be asked to provide attendance details for all participating children on the days when SFH activities are conducted.

#### Acceptability and feasibility of SFH

We have recently evaluated the above activities, related materials and training sessions for the appropriateness and acceptability of their content, layout and format through a series of focus group discussions with children and school teachers(37). We also spoke to parents and as a result of these discussions made minor but required modifications to the above. The delivery of SFH in our pilot was carried out by the SFH co-ordinator with the co-operation of school staff. Schools welcomed this initiative and were accommodating towards our SFH team to deliver these sessions. School staff also helped in retrieving promise forms and supporting relevant follow-up activities. Focus group discussions within schools highlighted broad acceptability and interest in the initiative. There are several other places in the UK where this scheme has been up and running and their reports suggest its wider acceptability(35;36). We expect the Black and Minority Ethnic (BME) population to be well represented in our sample. In fact our pilot study was carried out in an area with a significant South Asian community. Our Smoke Free Homes work in Pakistan and West Yorkshire has enabled us to develop Smoke Free materials in South Asian languages which have been evaluated for cultural appropriateness and acceptability. SFH coordinators will use prescribed methods of delivery using identical tools and materials. In our experience, it would be possible to deliver SFH in 25 schools in a standardised manner over a short period of time.

#### **Control Group**

Schools randomly allocated to the control group will not receive the SFH activities immediately. Children will of course continue with normal teaching and this will include the schools meeting the National Curriculum guidelines within Key Stage 2 of teaching children about developing a healthy safer lifestyle. If SFH is shown to be effective, schools in the control arm will be offered the SFH activities after 24 months when all participating children have left the primary schools and moved to secondary schools.

## Follow Up

All participating children will provide baseline data and will take part in the SFH activities if they are allocated to the intervention group, however only a sample of the participants will be followed up for the remainder of the trial. This sample will include a random sample of 90% of the children who test positive for cotinine at baseline and a random sample of 10% of children who test negative for cotinine at baseline. This sampling will be done using assigned unique identification number only. The CLASS trial is primarily focussed on investigating the effect of SFH on children who are exposed to second-hand smoke and therefore we are interested in the children who test positive for cotinine at baseline. However we need to inform parents and children who will not be followed up for the remainder of the trial that this is the case and thank them for their willingness to take part. It is important therefore that a mixture of children who test both positive and negative for cotinine are followed up in the trial so that parents cannot work out their child's cotinine test result. This will ensure complete anonymity and act as a further safeguard against identifying children with a positive cotinine test preventing schoolteachers or investigators from working out children's cotinine test results. Following up a random sample of 10% of children who test negative to cotinine at baseline will also allow us to investigate the proportion of these children who subsequently test positive for cotinine.

We will inform all parents and children by letter if they are to be followed up for the remainder of the trial or not and thank them for their participation in the trial.

The first follow up will take place 4 weeks post intervention. All children who remain in the trial will be asked to complete a children's survey (SO1, SO2, SO3, SO4) and provide a saliva sample (PO). Primary schools will oversee this data collection and will provide data on school attendance of participating children (SO5). As before, both survey and saliva samples will be anonymous containing no identifiable information other than the unique identification number.

We will ask primary schools to let us know which secondary school participating children move on to.

At follow up 2 (11 months post intervention), follow up 3 (24 months post intervention), follow up 4 (36 months post intervention, follow up 5 (48 months post intervention), and follow up 6 (60 months post intervention) we will ask all children who remain in the trial to complete a children's survey (SO1, SO2, SO3, SO4). We will ask for a random sample of children who remain in the trial to provide a saliva sample at each follow up. This is to test the validity of the children's self reported smoking status in the survey (SO2) at different ages. The size of the random sample will be decided after baseline data collection, at which point we will be able to investigate how well children's self reported smoking status is validated by the results of the cotinine tests. Primary schools will oversee

the data collection for children who remain at their school. Secondary schools will oversee the data collection for participating children who have moved to their school.

#### Follow-up in secondary schools

Children will inevitably move to secondary schools during the course of follow-up. We will track these children from school leaving lists and the local education authority database to their secondary schools. We will exclude secondary schools (and children) with less than 5 children from the original cohort. This strategy was adopted by Rudolph et al who studied prevalence of obesity and high BMI in a cohort study of school children carried out in Leeds, Yorkshire(42). They were able to track 87% of children (608 out of 694) from primary to secondary schools. After excluding those children who went to distant schools (<5 children from the original cohort), they were still able to approach 72% (500 out of 694) of children in the original cohort. After re-consenting, 348 (50% of the original cohort) agreed to take part in the second assessment. We expect higher follow up rates in our study as Rudolph et al carried this out as two separate studies and had to re-consent at the follow up.

### **Outcome measures**

#### **Primary outcome**

#### Salivary cotinine levels among children (Primary Outcome - PO)

Salivary cotinine measurement is a widely recognised method for detecting both active and passive smoking and has been used in several surveys and studies. It is measured by collecting saliva in the mouth and blowing it in a plastic container through a straw or by using a swab. The samples are subsequently analysed and a gas-liquid chromatography technique can detect cotinine levels as low as 0.1ng/ml. Based on cotinine measurements taken as part of the national household survey, various thresholds for active and passive smoking have been defined for different age groups(44). Salivary cotinine concentration, a sensitive biochemical marker, is strongly associated with the exposure to SHS at home(41). It has a half life of 20 hours(45) and therefore, we will ask for saliva samples to be given first thing in the morning to avoid any loss of sensitivity. The level of exposure according to the cotinine estimates can be grouped in several categories depending on the level of smoking and smoking restrictions at home. We will measure salivary cotinine levels at baseline for all participating children and at follow up 1, after the intervention, for all children who remain in the trial (90% of children who test positive at baseline and 10% of children who test negative at baseline) in both arms of the trial. At follow ups 2 to 6 we will measure salivary cotinine levels on a selected sample of the children who remain in the trial to test the validity of the report on their smoking status at different ages. We will analyse this as a continuous measure.

#### Secondary outcomes

#### Smoking restrictions at home (Secondary Outcome 1 - SO1)

We will assess the level of smoking restrictions at home through a questionnaire completed by participating children. We assessed the feasibility of this tool in our exploratory study and modified it accordingly. The assessment is based on two questions; (a) Do people in the house smoke in front of children? (b) Where do people smoke? Responses to question (a) will be assessed as a binary outcome. However, responses to question (b) will be grouped in one of three categories. Smoking takes place; (i) in any part of the house; (ii) in one room only; (iii) only outside the house. We will add additional questions to assess smoking restrictions on the visitors. Our assessment is similar to the approaches used by other researchers(23;46).

We acknowledge the gradual shift in the smoking behaviour in households in the UK and the importance of a complete smoking ban inside the house as a key objective. However, one of the researchers in our team identified key issues and challenges in implementing smoking restrictions at home(30). One of the considerations was that in poor households, having a gradual or stepped approach towards a 'smoke free home' is more acceptable. This is also applicable in single parent families and people living in tower blocks. Given our focus on deprived communities, we are going to assess and consider various levels of smoking restrictions at home as an acceptable outcome.

#### Children's attitude and behaviours towards smoking and intention to start (SO2)

We will use a five-point smoking uptake scale to assess children's attitude towards smoking and intention to start(23). It will be categorised as: (a) Non-susceptible non-smokers; (b) Susceptible non-smokers; (c) Early experimenters; (d) Advanced experimenters; (e) Established smokers. From the above, we will assess a difference in smoking uptake among children. We will carry out a saliva cotinine test on a selected sample to test the validity of the report on their smoking status.

#### Smoking behaviour of adults' (SO3)

We will assess the smoking behaviour of the adults living in participating children's households based on children's survey.

#### Quality of life (SO4)

Reduction in exposure to tobacco smoke may improve children's quality of life through the reduction of respiratory conditions (e.g., asthma attacks). We will use a short quality of life questionnaire with children for this purpose (PedsQoI)(48).

#### School attendance (SO5)

Reductions in SHS exposure may improve school attendance. We will collect data on school attendance from school registers.

## **Statistical Considerations**

#### **Proposed sample size**

We plan to recruit 50 schools (25 in each arm) in the study. We plan to recruit 40 children with positive cotinine tests at baseline and 4 children with negative cotinine tests at baseline from Years 4 and 5 from each of these schools. In total therefore we expect a sample size of 2200 children and their parents to be followed up until the completion of the trial. The primary outcome is to detect a difference in the salivary cotinine levels between children who test positive for cotinine at baseline (estimated 2000 children) and therefore we base our sample size on that as per convention. However, we believe that our sample size will have sufficient power to detect significant difference in secondary outcomes as well.

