#### Primary participants

All children in years 5 and 6 in the 2011/2012 school academic year will be eligible for the CLASS trial. Informed consent will be sought from parents/carers on an opt-out basis. After baseline data has been collected only a sample of children will be followed up for the remainder of the trial. This sample will include 90% of children who test positive for cotinine at baseline and 10% of children who test negative for cotinine at baseline. We aim to recruit at least 40 children with a positive cotinine test from each school.

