#### Sample Size Primary outcome

Our sample size estimation for the primary outcome is based on following assumptions:

- Significance level i.e.  $\alpha$  = 0.05 and 90% power
- Difference in the mean cotinine levels between control and intervention arms = 0.28 Standard Deviation = 1.38
- Intra-cluster correlation coefficient = 0.05
- Correlation between baseline covariate and outcome = 0.6

- 1. Effect size: We expect that the difference in the cotinine levels between children who are exposed to second-hand smoke and those who are not exposed is going to be more than 0.20. In addition, we expect that the difference in the cotinine levels between children who have different levels of exposure according to the smoking restrictions at home will also be more than 0.20. We believe that this is a clinically meaningful difference. We derive this difference from the research carried out by Ronchetti et al(18), who studied the relationship between cotinine levels among children and the place where the household members smoked while they were at home (specifically, if they smoked >4 cigarettes day-1 "at the dinner table" or "in the television room after dinner"). The smoking behaviour was classified in four categories accordingly. They found that the difference detected in the cotinine levels of children between different categories was greater than 0.20. Therefore, we are assuming that a shift of 0.20 in the cotinine levels in our study population will be of clinical significance; for example, this can be an important difference in the levels of exposure of children to SHS between adults smoking in one room only and not smoking inside the house. The calculations are based on an SD of 1.38 which would bring the detectable difference of 0.28 to 0.20 of a standard deviation. We think that 0.20 of a standard deviation is a relatively small effect to look for and in observational data is what we might expect to find.
- 2. Intra-cluster correlation coefficient is selected on the basis of what has been used for continuous outcomes in school based studies on tobacco, drug and alcohol use(49-51).

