- 3. Size of the cluster (children in each school): We plan to recruit 40 children from each school with a positive cotinine test as baseline. We believe that this is achievable based on the following assumption. In an average primary school in Yorkshire & Humber, we expect three classes of 30 children each in a year which will give us a potential recruitment pool of 180 per school. Given that 40% children are expected to be exposed to SHS, we should have at least 100 participating children to give us a sample of at least 40 children with positive cotinine levels from both years.
- 4. Correlation between baseline covariate and outcome: We assume a relatively conservative correlation co-efficient between baseline and outcome covariate of 0.6. Cook et al(45) shows a correlation of greater than 0.8 between pre- and post salivary cotinine levels, which if holds for our study, will significantly increase its power.
- 5. Attrition rate: In terms of attrition, for the primary outcome, we assume a very low attrition (<5%) in line with previous trials we have undertaken in schools. For our sample size calculations we have been deliberately conservative in our estimates; if we had a 15% attrition, which we think unlikely, then our sample size would be 1700, which would give us power to show a 0.20 difference in effect size. Even if we end up following only 25 children in each school then based on SD of 1.38, d = 0.28, alpha = 0.05, ICC = 0.05 and corr = 0.6 the power will be around 0.85. Clearly, if attrition is lower (likely) and the ICC is lower (likely) and pre and post test correlation is higher (likely) then we would have more power to show a smaller difference.
- 6. Design effect: The design effect we used here is 2.95 (i.e.,  $[40-1] \times 0.05 + 1$ ).

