## **Statistical analysis**

The analysis plan will include:

- Preliminary analysis consisting of a series of descriptive tables summarising; (a) basic characteristics of the data collected; (b) baseline characteristics of schools and children; (c) attrition rates; and (d) intra-cluster correlation coefficient for the outcomes. This will also include a comparison between participants with detectable levels of cotinine at baseline and zero levels of cotinine at baseline.
- A comparison of the means of the main outcomes at both cluster and individual level after adjusting for the cluster design. We will also adjust for the baseline characteristics and other covariates using generalised estimating equations.

We will only be measuring the salivary cotinine levels of a sample of children at follow up (90% of children who test positive for cotinine at baseline and 10% of children who test negative for cotinine at baseline).

Our principal analysis will be an adjusted analysis of salivary cotinine levels (for children who test positive for cotinine at baseline and remain in the trial – 90% of children who test positive for cotinine at baseline will remain in the trial). Consequently we do not need to adjust the main outcome for multiple testing. For all secondary outcomes we will adopt a more conservative p value (i.e., p = 0.01) to reduce the risk of a type 1 error. We will adjust for the minimisation variables and In terms of the secondary analyses we will adjust for minimisation factors and baseline measures if taken (e.g., quality of life). We will estimate a difference in the mean of salivary cotinine of all children irrespective of their smoking status.

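### The 40 cotinine-positive children per school are counted before the 90% follow-up sampling, so at the stated minimum the primary analysis has 1800 children, not 2000; power barely changes

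*Protocol*

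**What the plan says.** Proposed sample size (Protocol): "We plan to recruit 40 children with positive cotinine tests at baseline and 4 children with negative cotinine tests at baseline" per school. The following text concludes "In total therefore we expect a sample size of 2200 children and their parents to be followed up until the completion of the trial" and puts the positives available for the primary outcome at an estimated 2000.

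Sample Size Primary outcome, item 3, explains where the 40 comes from. With 40% of children expected to be exposed, "we should have at least 100 participating children to give us a sample of at least 40 children with positive cotinine levels", out of a potential pool of 180 per school. Item 6 uses 40 as the cluster size and obtains a design effect of 2.95. Item 5 gives 1700 children after 15% attrition.

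Primary participants, Follow Up, Outcome measures and Statistical analysis all describe a sampling step after baseline: a random 90% of positives and 10% of negatives stay in the trial. The principal analysis is confined to baseline positives who remain, and Statistical analysis repeats that "90% of children who test positive for cotinine at baseline will remain in the trial".

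On year groups, Primary participants says "All children in years 5 and 6 in the 2011/2012 school academic year will be eligible for the CLASS trial", and Trial Intervention agrees. The sample size sentence names Years 4 and 5.

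**The concern.** All participating children are tested at baseline, so 40% of 100 participants is the number who test positive before any sampling. The 90% step comes afterwards and never enters the sample size section. The 4 negatives, by contrast, can only be a count after sampling, because a school with 100 participants and 40 positives has 60 negatives. The 40 + 4 therefore appears to add an unsampled count to a sampled one. The figures of 2000, 2200, 2.95 and 1700 all rest on it, and so does the 2000 used as the base for long-term tracing in Sample Size Secondary outcomes.

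At stake are the stated size of the primary analysis and the recruitment target. A team that stopped at 100 participants or 40 positives in a school would believe the target was met while retaining 36.

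**Working it through.** **Inputs, all from the Protocol.** "Difference in the mean cotinine levels between control and intervention arms = 0.28 Standard Deviation = 1.38"; "Intra-cluster correlation coefficient = 0.05"; baseline-outcome correlation 0.6; alpha and power as in "0.05 and 90% power"; 25 schools per arm; exposure 40%; sampling fractions 90% and 10%. The Protocol does not say whether the test is two-sided; I assume that it is.

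**Reproducing the plan's figure.**
- Individually randomised n per arm = 2 × (1.960 + 1.282)² × (1.38/0.28)² ≈ 511.
- Design effect at 40 per school = 1 + 39 × 0.05 = 2.95. Factor for baseline adjustment = 1 − 0.6² = 0.64.
- 511 × 2.95 × 0.64 ≈ 965 per arm. 965/40 = 24.1, rounded up to 25 schools. 2 × 25 × 40 = 2000.

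So 2000 reproduces, and it needs 40 analysed positives per school.

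**Applying the sampling rule at the stated minimum.**
- Positives: 0.40 × 100 = 40 tested positive; 0.90 × 40 = 36 kept.
- Negatives: 60 tested negative; 0.10 × 60 = 6 kept.
- Primary analysis: 36 × 50 = 1800. Followed up: 42 × 50 = 2100. With the plan's own 4 negatives the total would be 40 × 50 = 2000. Neither is 2200.
- Design effect: 1 + 35 × 0.05 = 2.75.
- 15% attrition: 0.85 × 1800 = 1530. The plan's 1700 is 0.85 × 2000.

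**Power.** With m analysed children per school, SE = 1.38 × √[2 × DE × 0.64 / (25m)], and power = Φ(0.28/SE − 1.96).

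| Case | m | Total | DE | Power |
|---|---|---|---|---|
| As stated | 40 | 2000 | 2.95 | 0.910 |
| After 90% sampling | 36 | 1800 | 2.75 | 0.9005 |
| Sampling + 5% attrition | 34.2 | 1710 | 2.66 | 0.895 |
| Plan's 15% attrition | 34 | 1700 | 2.65 | 0.895 |
| Sampling + 15% attrition | 30.6 | 1530 | 2.48 | 0.883 |
| Plan's fallback | 25 | 1250 | 2.20 | 0.856 |

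At m = 36 the requirement is 511 × 2.75 × 0.64 ≈ 899 per arm, and 899/36 = 24.98 schools, so 25 per arm is only just enough.

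**Testing the other reading.** Suppose 40 and 4 are both counts after sampling. Then 40/0.9 = 44.4 must test positive, which needs 44.4/0.4 = 111 participants. That leaves about 67 negatives, of whom 10% is 6 to 7, not 4. The 2000 and 2.95 would then stand, but the 100 participants, the 4 negatives and the 2200 would not.

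**The case against.** The best defence is that 40 is a floor. Both Primary participants and item 3 say at least 40, and the pool is 180. If the whole pool took part, 40% would be 72 positives and about 65 kept. This stands: 1800 is what the stated minimum yields, not a forecast of what the trial will analyse. It does not repair the section, because the sample size section carries the minimum forward as if no sampling followed.

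The sentence can also be read as giving counts after sampling, since it leads directly to the number followed up. That would rescue 2000, 2.95 and 1700. It conflicts with item 3's derivation from 100 participants and still fails on the negatives and the total.

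The effect on the primary analysis is also small. That is correct. A reader might infer that the margin the Protocol calls conservative is exhausted. The document does not support this: item 5 already discloses a harsher case, 25 children per school with power around 0.85, and that figure reproduces at 0.856. Lower power can be produced by adding an allowance for unequal school sizes, but the Protocol gives no coefficient of variation, and that loss would not come from the sampling step.

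A reader might also see a conflict between following children to completion and the 72% and 50% retention figures. The former describes the intended cohort; the latter are expectations for long-term secondary outcomes. The primary analysis is at 4 weeks, with attrition assumed below 5%.

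**Conclusion.** The stated sample size is wrong as written, and the point is minor. At the stated minimum of 100 participants and 40 positives per school, the design yields 36 positives and 6 negatives per school, 1800 in the primary analysis and 2100 followed up, with a design effect of 2.75 and 1530 positives after 15% attrition. The shortfall in the primary analysis is 10%, but power falls by only about one percentage point, because clustering dominates the variance and rounding up to 25 schools per arm leaves some slack. The 90% target is just met before attrition (0.9005) and narrowly missed after it (0.895 at 5%, 0.883 at 15%).

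These figures assume a two-sided test, a normal approximation, equal school sizes and the Protocol's own inputs. A t reference with 48 degrees of freedom lowers both cases (0.899 at 40 per school, 0.889 at 36) and leaves the same one-point difference. The document does not support calling the trial underpowered.

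The year-group mismatch is clerical. Years 4 and 5 may describe the same children one school year earlier, and it has no bearing on the numbers.

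**What to change.** State in Proposed sample size whether 40 per school is before or after the 90% sampling. Then do one of the following.

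1. **Keep 40 analysed.** Set the baseline minimum at about 45 positives per school, which at 40% exposure is about 112 participants (62% of the pool of 180). The 2000, 2.95 and 1700 then stand. Change the negatives kept from 4 to about 7 and the total followed up to about 47 × 50 = 2350. The cost is about 12 × 50 = 600 more children surveyed and tested at baseline than the present minimum, and about 150 more followed up than the stated 2200.
2. **Keep the present minimum.** Restate 36 positives and 6 negatives per school, 1800 in the primary analysis, 2100 followed up, design effect 2.75 and 1530 after 15% attrition, with power 0.90, about 0.895 at 5% attrition and 0.88 at 15%. Change the tracing base in Sample Size Secondary outcomes to match: 72% of 1800 is 1296, in place of 1440 of 2000. This costs only wording and a slightly less favourable power statement.

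In either case, align the year groups in the sample size sentence with Years 5 and 6.
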